1.4.1.2 Preliminary Pharmacokinetic and Pharmacodynamic Data

Preliminary Pharmacokinetic Results

Preliminary PK data through a data cut-off date of 09 October 2015 are available, and summary statistics for select PK parameters are presented in Table 1.

Exposure to SBC-103 increased in a dose proportional manner across the doses tested (0.3, 1, and 3 mg/kg) based on the maximum observed serum concentration (C_{max}) and the area under the concentration-time-curve from time 0 to the last measureable time point (AUC_{last}) on Day 0 and at Week 12. Power analyses, in which the Ln AUC_{last} PK exposure was regressed against Ln Dose (0.3 to 3 mg/kg) across all subjects yielded a β value of 1.075 (95% CI: 0.865-1.29) at Day 0 following single dose (first dose) administration and 0.804 (95% CI: 0.537-1.07) at Week 12 following multiple dose administration QOW. These values were 1.12 (95% CI: 0.893-1.35) at Day 0 and 0.855 (95% CI: 0.617-1.10) at Week 12 for C_{max}.

The mean half-life ($T_{1/2}$) for SBC-103 increased from 0.14 to 0.29 hours and was independent of dose and time (Table 1). As shown in Table 1, accumulation (C_{max} and AUC_{last}) was observed at Weeks 12 and 24 in the 0.3 and 1 mg/kg dose cohorts. In contrast, no accumulation was observed at Week 12 in the 3 mg/kg dose group (R_{ac} =0.95 to 0.99).

			0.3 mg/k (N=3)	g		1 mg/kg (N=4)			3 mg/kg (N=4)	
Parameter	a	n	Mean (SD)	CV%	n	Mean (SD)	CV%	n	Mean (SD)	CV%
	Day 0	3	440 (94)	22%	4	1862 (374)	20%	4	5538 (2448)	44%
AUC _{last}	Week 12	3	782 (58)	7.4%	4 ^b	2789 (725)	26%	3 ^b	5299 (2659)	50%
(IIg•II/IIIL)	Week 24	3	630 (149)	24%	1	2703	NA	ND	ND	ND
	Day 0	3	250 (38)	16%	4	1073 (199)	19%	4	3617 (1960)	54%
C _{max} (ng/mL)	Week 12	3	433 (29)	6.6%	4 ^b	1571 (493)	31%	3 ^b	3231 (1315)	41%
(iig/iii2)	Week 24	3	333 (30)	9%	1	1424	NA	ND	ND	ND
	Day 0	1	0.29	NA	3	0.22 (0.04)	19%	3	0.14 (0.04)	28%
$T_{1/2}$	Week 12	2	0.21 (0.05)	22%	4 ^b	0.27 (0.13)	48%	2 ^b	0.28 (0.16)	59%
(1)	Week 24	1	0.19	NA	1	0.28	NA	ND	ND	ND
R _{ac} for	Week 12	3	1.77 (0.39)	22%	3 ^b	1.53 (0.29)	18.8%	3 ^b	0.95 (0.61)	63.5%
C _{max}	Week 24	3	1.34 (0.13)	9.5%	1	1.53	NA	ND	ND	ND
R _{ac} for	Week 12	3	1.81 (0.25)	14%	3 ^b	1.59 (0.11)	7.0%	3 ^b	0.99 (0.68)	68%
AUC _{last}	Week 24	3	1.44 (0.17)	12.0%	1	1.64	NA	ND	ND	ND
			Mean	Range		Mean	Range		Mean	Range
	Day 0	3	1.08	0.5-2.25	4	1.63	1.5-2.0	4	1.25	0.5-1.5
T_{max}	Week 12	3	1.67	1.5-2.00	4 ^b	1.25	1.5-1.5	3 ^b	2.00	0.5-2.5
()	Week 24	3	1.75	1.5-2.25	1	2.00	NA	ND	ND	ND

 Table 1:

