3.4 Study Endpoints

3.4.1 Primary Endpoint

The primary endpoint of this study is safety and tolerability of SBC-103 in subjects with MPS IIIB. The safety assessments will include the following:

- Incidence of AEs, SAEs, and IARs;
- Changes from baseline in clinical laboratory tests (hematology, serum chemistry, and urinalysis) and CSF findings (cell counts, glucose, and protein);
- Changes from baseline in 12-lead electrocardiograms (ECGs);
- Changes in vital signs during and post-infusion, relative to pre-infusion values;
- Physical examination findings;
- Use of concomitant medications/therapies;
- Assessment of ADAs, including seroconversion rate, time to seroconversion, and ADA titer by time point, peak ADA titer, and ADA titer status (positive/negative), and the effect of ADAs on the safety of SBC-103, including the relationship between ADA-positive subjects and the incidence of IARs.

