5.1.7 Vital Signs and Electrocardiogram

Vital signs, including pulse rate, respiratory rate, systolic and diastolic blood pressure (BP), and body temperature will be taken at the time points specified in the SOA. In addition, a baseline blood pressure measurement should be taken in triplicate prior to administration of SBC-103 at screening or prior to SBC-103 administration on either Day 0 in Part A or the subject's the next scheduled infusion. The baseline BP measurement should be done as follows:

- Ensure the subject is relaxed or distracted.
- Obtain 3 separate BP measurements.
 - The same arm should be used for each reading.
 - The right arm is preferred for these repeat BP measurements for consistency and comparison with standard tables and, because of the possibility of coarctation of the aorta, which might lead to false (low) readings in the left arm.

- \circ Each reading should be taken on the same day >15 minutes apart.
- The same suitable equipment should be used for each reading.
- Each measurement should be recorded in the subject's source records and in the CRF

On Day 1 in Part A, vital signs will be taken prior to hospital discharge. During dosing visits vital signs will be taken pre-dose (within approximately 30 minutes), approximately every 15 minutes during infusion and approximately every 15 minutes for 2 hours after completion of the infusion. Vital signs should also be obtained after the lumbar puncture is completed as per the standard of care. In Part B, the duration of post-infusion vital signs monitoring may be shortened to 1 hour starting with Week 54, provided that there is no occurrence of IARs during the infusion. In Part C, the duration of post-infusion vital signs monitoring may be shortened to 1 hour starting with Week 26 of Part C, provided that there is no occurrence of IARs during the infusion.

Every effort will be made to collect a 12-lead ECG during the time points specified in the SOA; 12-lead ECGs will be collected in triplicate during Part A of the study only. ECGs will be reviewed by the Investigator, or designee, and any abnormalities will be specified as clinically significant or not clinically significant.

Due to the behavioral issues typical of subjects with MPS IIIB, ECG assessments may not be able to be completed, but should be attempted whenever possible.

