6 STUDY TREATMENTS

6.1 Treatments Administered

Part A (Initial Therapy)

In Part A, all subjects in each dosing cohort (0.3 mg/kg, 1 mg/kg, 3 mg/kg) will receive SBC-103 administered by IV infusion QOW for 24 consecutive weeks. Infusions must be administered at least 10 days apart. All study visits will be scheduled relative to Day 0.

Part B (Therapy at 1 and/or 3 mg/kg)

For eligible subjects, dosing in Part B may not be re-initiated sooner than 4 weeks and no greater than 4 weeks and 3 days after the last dose administered in Part A (See SOA). Subjects who received doses of either 0.3 mg/kg or 1 mg/kg during Part A may escalate to the next higher dose of SBC-103 considered to be safe by the Sponsor and SRC with their first dose in Part B or at any time thereafter. Subjects who received doses of 0.3 mg/kg in Part A may be considered for a second dose escalation to 3 mg/kg at any time during Part B provided that they have tolerated at least 2 doses of 1 mg/kg in Part B (see Section 3.1.2).

In Part B, if a subject misses ≥ 3 consecutive infusions, additional assessments will be required prior to resuming dosing, including safety labs (hematology, chemistry, coagulation, urinalysis and pregnancy test, where applicable), and serum and urine HS. If ≥ 6 consecutive infusions are missed, additional assessments, including lumbar puncture for CSF collection, may be required prior to resuming dosing as determined by the Sponsor in consultation with the investigator. The next scheduled lumbar puncture would not be necessary if ≤ 2 months have elapsed since the previous lumbar puncture.

Part C (Therapy at 5 and/or 10 mg/kg)

Dosing in Part C may start as soon as a subject is eligible (Section 4.3.4) and according to the schema outlined in Section 3.1.3. Therefore, each subject's duration of treatment and assessments in Part B may vary. Once a patient is dose escalated in Part C, the study visit schedule is reset to Day 0 Part C (Day 0C). In Part C, subjects will be randomized such that at least 1 subject from each cohort assigned in Part A will receive SBC-103 at 5 mg/kg and at least 1 subject from each cohort assigned in Part A will receive SBC-103 at 10 mg/kg. Thus each of the assigned dose levels from Part A will be represented in each of the 2 dose levels being studied in Part C. Infusions must be administered at least 10 days apart. All study visits in Part C will be scheduled relative to Day 0C.

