6.6.2 Administration of Study Drug

All infusions must be administered under close supervision of the Investigator, or designee. Study drug should not be infused with other products in the same infusion tubing, as the compatibility of SBC-103 in solution with other products has not been evaluated. It is recommended that all infusions of study drug be administered using in-line filtration with a low protein binding 0.2 micron filter.

The recommended duration of the infusion is 2 hours at a constant rate. The protocol allows for a change in rate should the patient experience an IAR. At the discretion of the investigator and in consultation with the sponsor, in circumstances such as a prior IAR or other like situations where patient safety is a concern, an extended duration of infusion or a variable rate is acceptable. If the infusion is not well tolerated, the infusion rate may be decreased or interrupted as noted in Section 7.1.3 and Section 6.2. All changes to infusion rate must be carefully recorded in the CRF, including the start and stop time of each rate change.

Refer to the IMP Manual for detailed instructions on the administration of SBC-103.

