Mild Reaction Common • Hyperemia (flushing) • Lightheadedness • Nausea • Mild chest discomfort (tightness) Less Common • Fever and/or shivering • Palpitations • Headache • Irritability (especially in young children)	 Slow infusion rate by 50% Increase infusion time in accordance with institutional standard of care Administer oral anti-pyretic and/or antihistamine Once the event has resolved, the infusion should continue at reduced rate for a minimum of 30 minutes before infusion is increased to 75% of original rate Decrease infusion rate by a further 25% if symptoms persist If symptoms continue despite rate reduction, stop infusion Pre-treat with oral antihistamine and antipyretic prior (approx. 1.5 hours) to next infusion eg, diphenhydramine 25-50 mg by mouth and acetaminophen 650 mg by mouth
 Hyperemia (flushing) Chest discomfort Itching and/or raised urticarial rash Severe headache Gastrointestinal symptoms, vomiting, diarrhea, abdominal cramping 	 Give antihistamine intravenously and consider IV steroids in accordance with institutional standard of care Give any prescribed inhaler treatment if appropriate Collect serum for analysis of tryptase 1-3 hours after the IAR onset and another serum sample for tryptase and ADA during the next study visit (≥4 days after the IAR) prior to the infusion. Pre-treat with oral antihistamine and antipyretic prior to next infusion Skin testing may be considered
 Severe Reaction Clinically significant cardiovascular effects (hypotension defined as a decline approaching 20-30% of their preinfusion value without alternative etiology (agitation, pain, fluid overload, dehydration) Respiratory symptoms: Significant shortness of breath, stridor, wheezing, laryngeal oedema, swelling of tongue. Cardiac arrhythmias Anaphylactic/Anaphylactoid shock with hypotension and circulatory collapse 	 Stop infusion Give oxygen, if available Give intramuscular injection of epinephrine (adrenaline) Give antihistamines intravenously and steroids intravenously Collect serum sample for tryptase 1-3 hours after the IAR onset and another serum sample for tryptase and ADA during the next study visit (≥4 days after the IAR) prior to the infusion. Skin testing may be considered Dosing of the subject will be suspended until the SRC has completed review of the IAR, and any other relevant safety data (Section 6.2)

Table 9:Guidelines for the Management of IARs

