14 APPENDICES

14.1 Appendix A: Schedule of Study Assessments (Part A, Initial Therapy)

	Schedule of Study Assessments															
	Part A: Initial Therapy												Time Off			
Assessments	Screening	Day 0***	Day 1	Week 2	Week 4	Week 6	Week 8	Week 10	Week 12	Week 14	Week 16	Week 18	Week 20	Week 22	Week 24	Week 26
Visit Window (Days)*	-28 to 0**	-4 to 0		±5	±5	±5	±5	±5	±5	±5	±5	±5	±5	±5	±5	
Informed Consent/Assent	Х															
Inclusion/Exclusion Criteria	Х															
Medical History/ Demography	Х															
Physical Examination	Х	X ^P	Х		X^{P}		X^{P}		X ^P		X ^P		X^{P}		X ^P	
Height and Weight	Х	X ^P			X ^P		X ^P		X ^P		X ^P		X ^P		X ^P	
Vital Signs ¹	Х	Х	Х	Х	Х	Х	Х	Х	Х	Х	Х	Х	Х	Х	Х	
12-lead ECG (Triplicate ²)	Х	X ^P							X ^P						X ^P	
FDNA	Х														Х	
Vineland-II, BSID-III, KABC-II, BOT-2 Brief Form, CSHQ, CCC-2, SBRS, ZBI 12-item, SF-10 ³	X ³														X ^P	
NAGLU Enzyme Activity ⁴	Х															
NAGLU Genotype ⁵	Х															
DNA Sample ⁶	Х															
Hematology, Serum Chemistry (including Coagulation ⁷), Urinalysis ⁸	Х	X ^P	х		X ^P		X ^P		X ^P		X ^P		X ^P		X ^P	
Pregnancy Test (Urine) ⁹	Х	X ^P			X ^P		X ^P		X ^P		X ^P		X ^P		X ^P	
Serum and Urine Heparan Sulfate (Total and NRE) ¹⁰	Х	X^{P}			X ^P		X ^P		X ^P		X ^P		X ^P		X^{P}	
Serum Ferritin and Chitotriosidase ¹¹	Х	X^{P}			X^P		X^P		X ^P		X ^P		X ^P		X^P	
Plasma Glutamic Acid and Glycine ¹¹	Х	X^{P}			X^P		X^P		X ^P		X ^P		X^P		X^P	
Serum Biomarkers (Exploratory, including IgG and Inflammatory Markers)		X^{P}			X ^P		X ^P		X ^P		X ^P		X ^P		X ^P	
Blood Pharmacokinetic Profile ¹²		Х							X						Х	
SBC-103 ADA ¹³		X ^P			\mathbf{X}^{P}		\mathbf{X}^{P}		X ^P		X ^P		X ^P		$\mathbf{X}^{\mathbf{P}}$	

Page 100 of 121

	Schedule of Study Assessments															
						Pa	rt A: Ini	tial Ther:	apy							Time Off
Assessments	Screening	Day 0***	Day 1	Week 2	Week 4	Week 6	Week 8	Week 10	Week 12	Week 14	Week 16	Week 18	Week 20	Week 22	Week 24	Week 26
Visit Window (Days)*	-28 to 0**	-4 to 0		±5	±5	±5	±5	±5	±5	±5	±5	±5	±5	±5	±5	
General Anesthesia/Sedation ¹⁴		X^{P}							X ^P						X ^P	
Lumbar Puncture ^{7,14,15}		X ^p							X ^P						X ^P	
Heparan Sulfate (Total and NRE) in CSF		X ^P							X ^P						X ^P	
Calbindin D, HGF, Tau, pTau, Amyloid β , Albumin, IgG in CSF ¹⁴		X ^P							X ^P						X ^p	
Glutamic Acids and Glycine in CSF		X ^P							X ^P						X ^P	
Routine Findings (Cell Counts, Glucose, Protein) in CSF		X ^P							X ^P						X ^P	

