SBC-103 in CSF		X ^P							X ^P						X ^P	
Structural and Diffusion MRI ¹⁴		X ^P													X ^P	
SBC-103 Dosing		Х		Х	Х	Х	Х	Х	Х	Х	Х	Х	Х	Х	Х	
Telephone call ¹⁶				Х	Х	Х									Х	
Part B Eligibility Assessment																х
Adverse Events ¹⁷							CC	ONTINUC	OUS							
Concomitant Medications ¹⁸							CC	ONTINUC	OUS							

Key: ADA = anti-drug antibodies; BOT-2 Brief Form = Bruininks-Oseretsky Test of Motor Proficiency, Second Edition, Brief Form; BSID-III = Bayley Scales of Infant and Toddler Development, Third Edition; CCC-2 = Children's Communication Checklist, Second Edition; CSF = cerebrospinal fluid; CSHQ = Children's Sleep Habits Questionnaire; ECG = electrocardiogram; FDNA = Facial Dysmorphology Novel Analysis; HGF = hepatocyte growth factor; IgG = immunoglobulin G; KABC-II = Kaufman Assessment Battery for Children, Second Edition; MRI = magnetic resonance imaging; NAGLU = alpha-N-acetylglucosaminidase; NRE = non-reducing end; SBRS = Sanfilippo Behavior Rating Scale; SF-10 = 10-item Short Form Health Survey for Children; Vineland-II = Vineland Adaptive Behavior Scales, Second Edition; ZBI = Zarit Burden Interview, 12-item.

* All study visits will be scheduled relative to Day 0: infusions must be administered at least 10 days apart.

** Subjects who are unable to complete all Screening procedures within 28-day window may be re-screened. See Section 4.7.

*** Day 0 assessments may be completed over 5 days (starting on Day -4) provided that all eligibility assessments are completed prior to the commencement of any Day 0 procedure (ie, any invasive procedures, including general anesthesia or sedation, lumbar puncture, and MRI). Subjects will be monitored for at least 24 hours in an in-patient setting at the Day 0 visit. Documentation/confirmation of eligibility must be provided to the Sponsor and is subject to Sponsor review and agreement. At Day 0, the lumbar puncture (including the initiation of sedation/anesthesia) shall not commence until the site receives the coagulation results, confirms that a subject continues to meet eligibility, and provides such documentation to the Sponsor for review and agreement.

X^P Assessments to be performed pre-dose.

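### Every scheduled 12-lead ECG in Parts A and C is pre-dose (or at Screening) and Part B timing is unspecified, so the ECG component of the primary safety endpoint cannot show an acute infusion effect in Part A or at 5 or 10 mg/kg

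*Protocol*

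**What the plan says.** Protocol section 3.4.1 lists "Changes from baseline in 12-lead electrocardiograms (ECGs") as one component of the primary endpoint, without restricting it to any study part. Section 5.1.7 does not fix the timing itself: "Every effort will be made to collect a 12-lead ECG during the time points specified in the SOA". The timing is therefore whatever Appendices A to D show.

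In those tables a mark of X with superscript P means "Assessments to be performed pre-dose". The ECG rows of Appendices A and D carry that mark at every visit except Screening. The ECG rows of Appendices B and C carry a plain X, although other rows in the same tables carry the superscript. Day 1 of Part A and Day 1C of Part C have physical examination, vital signs and laboratory tests, but no ECG.

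On exposure, section 1.4.1.2 reports that mean half-life "for SBC-103 increased from 0.14 to 0.29 hours and was independent of dose and time". Section 6.6.2 states "The recommended duration of the infusion is 2 hours at a constant rate", and section 6.1 states "Infusions must be administered at least 10 days apart".

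During an infusion, section 5.1.7 schedules vital signs at about 15-minute intervals, continuing for 2 hours afterwards (1 hour later in the study if there was no infusion reaction).

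**The concern.** This is a first-in-human paediatric study, and the protocol itself treats acute cardiac events as possible: section 7.1.3 names "Cardiac arrhythmias" among the features of a severe infusion reaction. An ECG recorded just before a dose, long after the previous one has left the serum, would look normal even if the infusion briefly disturbed conduction or repolarisation.

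Two uses of the data are affected. First, section 8.4 plans to summarise ECG change from baseline by dose cohort, and a clean summary could be read as covering acute effects. Second, the decisions to continue dosing and to escalate (sections 3.1.1.1 and 3.1.3.1) rest on safety data that contain no scheduled ECG taken under exposure.

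**Working it through.** **1. The ECG marks, read row by row.** For Weeks 1C to 26C the column positions are taken from the copy of the schedule in SAP section 9.1.4.

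| Part | Visits with an ECG | Mark | Pre-dose or before any drug |
|---|---|---|---|
| A (Appendix A) | Screening, Day 0, Week 12, Week 24 | Screening plain, the other three X^P | 4 of 4 |
| B (Appendices B, C) | Weeks 36, 52, 78, 104, 130, 156 | plain X | 0 of 6 so marked |
| C (Appendix D) | Day 0C, Weeks 2C, 12C, 24C, 52C, 78C, 104C, 130C, End of Treatment | X^P | 9 of 9 |

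Screening and Day 0 precede any drug, and Day 0C is the Part C baseline. The post-baseline ECGs are therefore 2 in Part A and 8 in Part C, all pre-dose. Week 130C is unlikely to be reached, since SAP section 4 puts Part C at 90 to 110 weeks; that leaves 7.

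**2. The protocol's half-life range.** Table 1 gives eight means or single values: 0.29, 0.22, 0.14, 0.21, 0.27, 0.28, 0.19 and 0.28 h. Their minimum and maximum are 0.14 and 0.29 h, which reproduces the stated range. In minutes: 0.14 × 60 = 8.4 and 0.29 × 60 = 17.4.

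These are means. The 3 mg/kg Week 12 cell (n = 2, mean 0.28, SD 0.16) implies individual values of 0.28 ± 0.16/√2 = 0.167 and 0.393 h, or 10.0 and 23.6 minutes. No half-life is given for 5 or 10 mg/kg.

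**3. Exposure at a pre-dose ECG.** The shortest gap is 10 × 24 = 240 h. Taking the 10 days from the start of one infusion to the start of the next, and subtracting the 2 h infusion, leaves 238 h.

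| Half-life | Half-lives elapsed in 238 h |
|---|---|
| 0.29 h (largest mean) | 238 / 0.29 = 821 |
| 0.393 h (longer value in the n = 2 cell) | 238 / 0.393 = 606 |
| 12 h (assumed, far above anything reported) | 238 / 12 = 19.8, leaving 2^−19.8 ≈ 1 × 10⁻⁶ |

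Serum exposure at these recordings is effectively nil, and the missing half-life at 5 and 10 mg/kg does not change that.

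**4. When an ECG would be under exposure.** The time to fall to 1% of the end-of-infusion level is half-life × log₂(100): 0.29 × 6.64 = 1.9 h, or 0.393 × 6.64 = 2.6 h. Mean T_max in Table 1 runs from 1.08 to 2.00 h, that is, within or at the end of the 2 h infusion. An ECG at end of infusion would be near peak; one taken more than about 2 to 3 h later would not be under serum exposure.

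**5. Which decision a Week 2C recording could reach.** Day 0C is the first Part C dose and Week 2C the second. Under section 3.1.3.1, opening 10 mg/kg depends on one subject completing the first two doses at 5 mg/kg. Continuing and expanding each dose level depends on 24-hour data after the first dose. A Week 2C end-of-infusion ECG could inform the first decision but not the second.

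**The case against.** The strongest reply is that serum half-life is the wrong yardstick for a trough ECG. The enzyme is meant to act in lysosomes after uptake (sections 1.2 and 1.3). The cardiac finding reported in section 1.3 is vascular and perivascular inflammation in rats after repeated 10 mg/kg dosing, and most of the findings in that study had only partly reversed two weeks later. Repeated trough ECGs against baseline are a sensible way to look for that kind of change. This stands. A reader might infer that the scheduled ECGs carry no information about the drug; the documents do not support that.

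A reader might also infer that the ECG component never captures the heart under exposure anywhere in the study. That goes too far. The endpoint covers all parts, and the plain marks in Part B allow a recording during or after infusion, though they do not require one.

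Other components of the same endpoint do look at the acute period: frequent vital signs, infusion reactions up to 4 hours after infusion, and in Part A a 24-hour in-patient stay with a Day 1 examination. This stands in part, because pulse and blood pressure do not show conduction or repolarisation.

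The documents cite no acute electrophysiological signal for SBC-103, and the arrhythmia entry sits in general guidance on infusion reactions. That is correct. The point is what the schedule could detect, not that an effect exists.

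Pre-dose timing also has a practical basis. All three dosing-visit ECGs in Part A and 8 of 9 in Part C fall on visits with anaesthesia or sedation scheduled, and section 5.1.7 warns that behaviour may prevent an ECG. Week 2C is the exception, with no sedation scheduled.

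Finally, SAP sections 5.2.4.2 and 7.3.3.3.2 leave ECG analyses out of the study report. That limits the effect on the report, but it does not supply the missing input to the escalation decisions.

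**Conclusion.** The point holds in a limited form. In Parts A and C all 13 scheduled ECGs (4 + 9) are at Screening or pre-dose, and all 10 post-baseline ones (2 + 8) are troughs. They can show persistent or cumulative change, but not an acute effect in Part A or at 5 or 10 mg/kg. In Part B the timing is open, so an on-exposure recording at the doses given there is possible but not assured, and its summaries may mix pre-dose and post-dose recordings.

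This rests on the schedule marks being followed, on the minimum 10-day interval, and on a half-life at 5 and 10 mg/kg that is not many times longer than at 0.3 to 3 mg/kg (even 12 h would leave the conclusion intact). An unscheduled ECG prompted by a reaction remains possible. The gap is modest and cheap to narrow. It is not evidence of a missed cardiac effect.

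**What to change.** In Appendix D, move the existing Week 2C ECG from pre-dose to end of infusion, alongside the vital signs already taken then. Keep Day 0C pre-dose as the Part C baseline, and leave the ECGs from Week 12C onward as troughs. Each Part C subject would then have one on-exposure ECG (up to 5 at 5 mg/kg and 6 at 10 mg/kg), with no recording added. The data reviewed after the first two doses at 5 mg/kg, before 10 mg/kg is opened, would include one, provided the child tolerates the recording and the Safety Review Committee's data package includes ECGs.

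The cost is that the only early trough ECG after the new dose is lost, and the first-dose 24-hour review still has no post-dose ECG. The comparison also sets a Week 2C recording without sedation against a baseline from a visit where sedation is scheduled, but that is already so under the current timing.

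Moving the Part A Day 0 ECG to end of infusion is not recommended. It would give up the same-day baseline, and by 20 November 2015 all 11 enrolled subjects had passed that visit (section 1.4.1), before the protocol version of 21 January 2016.

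Any statement of no ECG signal from Part A should be limited to trough recordings. The same limit applies to Part C wherever the ECGs were recorded on the existing schedule.
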